6.5.1 Contract with sites

Request for the study

The request will be made to the medical institutions with a history of prescribing belzutifan and otherwise meet the criteria for participation. The objective and design of the study will be explained to the investigator in charge of the study and/or other staff of the institutions by Medical Representative (hereinafter, MR).

Contract with the sites

If the medical institution or investigator agrees to participate in the study in response to the request, a contract will be made in writing with the head of the institution (hospital director, etc.) after following the necessary process of the medical institution (e.g., IRB approval).

Study period

The study period at each site will be the period set out in the contract, which includes the period of enrollment, treatment, follow-up and (e)CRF collection.

6.5.2 Informed Consent

According to Japanese law, obtaining consent for participation and obtaining approval from the IRB/EC is not mandatory. It is legally required to collect information and submit them to the PMDA (Pharmaceuticals and Medical Devices Agency) even for cases where consent has not been obtained. Therefore, we obtain consent for the publication of survey results at the time of informed consent. If consent for publication cannot be obtained, the case is excluded from publication.

- 1) The investigator / program coordinator in charge of the study will confirm eligibility and explain to the subject or his/her legally acceptable representative the objective of the study, the information to be collected through the study (including the information of the subject's drug treatment and test results, etc.) and the uses of the study results (including presentation at an academic conference, etc. and publication, etc. by the sponsor of the survey) and obtain the written consent for the publication of study results from the subject or his/her legally acceptable representative.
- 2) In obtaining the consent for the publication of study results, the signature and date must be obtained from the subject or his/her legally acceptable representative in the consent form along with the signature and date by the person who has explained the study.

- 3) The investigator in charge of the study will give the subject or his/her legally acceptable representative a copy of the signed and dated consent form under the above (2) before the subject registers in the study.
- 4) The subject or his/her legally acceptable representative should be informed in a timely manner if new information becomes available that may be relevant to the subject's willingness to publication. The communication of this information will be adequately documented.

6.5.3 Subject registration at the site

The investigator shall enter the required information (anonymized ID number¹, sex, target tumor type, the start date of belzutifan administration, etc.) into the registration form of the EDC system and submit the form for patients meeting the inclusion/exclusion criteria.

Subjects may be prospectively identified and registered/enrolled at the time of treatment initiation or retrospectively identified and registered/enrolled after treatment initiation but before the end of the registration period.

All subjects who meet the eligibility criteria for this study at contracted sites will be registered until notified by the sponsor that registration has been terminated. The registration will continue until the target number of subjects (n=410) has been reached.

6.5.4 Subject observation

The treatment period is defined as the period from the start date of belzutifan administration until the date of the last administration. The observation period is defined as 12 months (52 weeks) from the start date of the administration. Adverse events will be collected throughout the treatment period and for 30 days following discontinuation of belzutifan treatment. However, the total follow-up period will not exceed the observation period [1 year (52weeks) from the first belzutifan treatment date].

Rationale for the observation period

In the 005 study, the median time to the first occurrence of hemorrhage was 84 days (range: 2 to 728 days), and the median time to the first occurrence of fractures was 277.5 days (range: 5 to 639 days). Additionally, most of the adverse events considered for safety concerns in this survey occurred within three months of the start of administration. To confirm the occurrence status (incidence rate, severity, treatment details, etc.) of these events, a 12-month (52-week) observation period was set.

¹ Any number or symbol that allows the investigator to identify the patient (no patient information such as medical record number required)

6.5.5 Safety endpoints and effectiveness endpoints collection

The investigator / program coordinator at each site will monitor for the occurrence of any endpoints specified within this protocol through the on-site visit, scheduled contacts, e-mails, telephone calls, and/or review of the medical records during the treatment and observation periods.

6.5.6 Entry into the case report form and transmission

The investigator will document the information collected during the treatment and observation period in the (e)CRF.

For the subjects for whom follow-up becomes difficult (e.g., transfer to other hospital, etc.), the information which can be collected until the last observation will be documented in the electronic (e)CRF.

6.5.7 Confirmed all subject at contracted site

To ensure the completeness of subject extraction at the site, after the end of the case registration period, each investigator will confirm that the studied cases are all cases in which belzutifan was administered at their own site / department using the “All Case Confirmation Form”.

6.5.8 Confirmation of inconsistency to the investigator in charge (correction request) of the registration form and the case report form and follow-up survey

- 1) At the time of receipt of the registration form and the surveillance form, post marketing surveillance MSD management department will verify the entered contents; if a correction request is necessary or resurvey is necessary, they will ask the investigator in charge of the surveillance to add, correct, and confirm the information.
- 2) Pregnant and lactating subjects must be followed up to the extent possible with the cooperation of the investigator in charge of the study and the subjects.
- 3) In addition to item 2) above, if an event that MSD is monitoring for information (i.e., hypoxemia etc) is reported, we will conduct follow-up investigations in collaboration with the investigator and the subjects whenever possible.

6.5.9 Management of progress of the study

- 1) Post marketing surveillance MSD management department must make efforts to promote the study in a systematic manner, utilizing the management schedule that describes the progress of the study.

- 2) The Chief administrator of Post Marketing studies of MSD will confirm whether the study is progressing smoothly and give appropriate instructions to each of the relevant departments in the company as necessary.

6.5.10 Study system and methodology

The study will be conducted with the use of Electronic Data Capture (EDC) system by means of a central registration method.

6.6 Study Item

As possible, all the data for the following items will be collected in this study.

Category	Collection item
Subject characteristics and indication(s) for use	
 • Anonymized ID Number • Sex • Month/year of birth (or Age at the start of belzutifan administration) • Indication for use • Start date of treatment with belzutifan • Inpatient/outpatient (at the start of belzutifan administration) • Height • Weight • Smoking status • Pregnancy status at the start of administration of belzutifan (female only) • Lactation status at the start of administration of belzutifan (female only) • Karnofsky Performance Score (KPS) at the start of administration of belzutifan • Eastern Cooperative Oncology Group (ECOG) Performance status at the start of administration of belzutifan

Category	Collection item
Medical history and co-morbid condition	
 • For select conditions (e.g., liver dysfunction, renal dysfunction, respiratory diseases, cardiac diseases, osteoporosis, and others), whether they were previously present and cured versus an ongoing co-morbidity will be recorded, as well as some details on the disease/severity. 
For hepatic impairment, Grade information will also be collected using the Child-Pugh² classification. Please refer to Table 2 and Table 3 for details on the grading.

Condition of RCC before belzutifan Administration	
 • Date of diagnosis (at initial diagnosis, at most recent recurrence diagnosis) • TNM Staging System (at initial diagnosis, at most recent recurrence diagnosis) • International Metastatic Database Consortium (IMDC) Risk Classification • Histological subtype (i.e., ccRCC vs nccRCC) • Site of recurrence or metastasis at most recent diagnosis • Treatment line at the time of starting administration of belzutifan (including belzutifan)
Prior Treatment for RCC before belzutifan Administration	
 • Prior medications • Prior radiotherapy • Prior surgeries • Other prior treatments
Treatment of belzutifan	
 • Initiation date of belzutifan • The date of any dose for belzutifan and stop date of belzutifan after Day 1 • Daily dose • Action taken with belzutifan (e.g., dose interruption/daily dose change) • Reason for dose interruption/reason for daily dose change (if applicable)

² [1]

Category	Collection item
Concomitant medications	
 • Presence or Absence of concomitant medications 
For any concomitant medications:
 
 • Name of concomitant medication • Daily dose • Route of administration • Duration of medications (Start date and stop date of administration) • Reason for use
Non-pharmacological Concomitant therapies	
 • Presence or Absence of concomitant therapies 
For any concomitant therapies:
 
 • Detail of concomitant therapies (Radiotherapy, Surgical procedure, Other therapy) • Duration of treatment (Start date and stop date of therapy) or date of procedure • Reason for therapies
Effectiveness	
Investigators will assess and report effectiveness as detailed below. Timing of these assessments will based upon routine follow-up evaluations.
 
 • Presence or absence of effectiveness evaluation 
For any effectiveness evaluations:
 
 • Assessment method Assessment methods will follow the standard procedures of each site, including but not limited to Response Evaluation Criteria in Solid Tumors guideline version 1.1 (RECIST v.1.1). Whenever possible, the same assessment method should be used consistently for each individual patient. • Tumor response assessment (Date of assessment, Tumor response)

Category	Collection item
Status on the date of last observation	
 • Last observation date • Condition on the last observation date • Administration status of belzutifan after 12 months of observation following the start of administration • Other treatments for RCC within 30 days after the last administration of belzutifan³ • Date of discontinuation of belzutifan (if applicable) • Reason for discontinuation (if applicable) • Presence or absence of intracranial lesions during the observation period • Occurrence of intracranial hemorrhage up to 30 days after the last dose of belzutifan
AEs	
 • Presence or Absence of adverse event 
For any adverse event:
 
 • Adverse event term • Onset date • Seriousness • Reason for seriousness • Causal relationship by investigator with belzutifan • Factors other than belzutifan • Maximum Common Terminology Criteria for Adverse Events (CTCAE) grade • Outcome / Date of Outcome • Action taken with belzutifan after the onset of the adverse event • With or without re-administration of belzutifan • Improvement of adverse events after de-challenge of belzutifan • Recurrence of AEs after re-administration of belzutifan • Cause of Death and Autopsy Details (if applicable) • Procedures and laboratory test⁴ data / test details. • Safety Considerations 
[Hemorrhage]
 
 • Site of hemorrhage

³ The total follow-up period will not exceed the observation period [12 months (52 weeks) from the first belzutifan treatment date]

⁴ Clinical laboratory values/tests for anemia (Hb), hypoxia (SpO₂) and hemorrhage (PT, PT/INR, APTT, platelet count)

Category	Collection item
	
 • Volume of hemorrhage (only for intracranial hemorrhage, if applicable) • Comorbidities potentially contributing to hemorrhage • Use of drugs that affect the coagulation system (anticoagulants, antiplatelet agents, and NSAIDs) • Laboratory test [prothrombin time (PT), PT/INR, APTT, Platelet count], if applicable 
[Fracture]
 
 • Site of fracture • Fracture at the metastatic site 
[Anemia]
 
 • Use of erythropoiesis-stimulating agents following the onset of the event. • Use of blood transfusion following the onset of the event. • Laboratory test (Hb) 
[Hypoxia]
 
 • Symptoms/signs observed at the time of onset • Oxygen administration following the onset of the event • SpO₂
Laboratory data (only if related to adverse events)	
 • Name of laboratory test⁵ • Date of laboratory test performed (before the first administration of belzutifan, after the initiation of administration) • Laboratory results

⁵ Clinical laboratory values/tests other than those for anemia (Hb), hypoxia (SpO₂), and hemorrhage (PT, PT/INR, APTT, platelet count)

Category	Collection item
Test	
 Name of test (including imaging) Date of test performed Test result/findings

Table 2 Child-Pugh classification

Score	1 point	2 points	3 points
Hepatic Encephalopathy	None	Mild (Grade I · II)	Coma (Grade III≤)
Ascites	Absent	Slight	Moderate
Serum Bilirubin (mg/dL) ⁶	<2.0	2.0-3.0	3.0<
Serum Albumin (g/dL)	3.5<	2.8-3.5	<2.8
Prothrombin Time Activity (%)	70<	40-70	<40
INR	<1.7	1.7-2.3	2.3<

Table 3 Child-Pugh Total Score

Class	Total Score
Class A	5-6 points
Class B	7-9 points
Class C	10-15 points

[1]

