5.2 Secondary Objectives

- 1) The overall safety of belzutifan, including safety concerns, in subjects with RCC
- 2) The effectiveness of belzutifan in subjects with RCC

To address the Secondary Objectives, the following points will be addressed:

- a) To describe the patient demographic and baseline clinical characteristics in;
 - In the registered subjects
 - in the safety evaluation group
 - by presence/absence of any AEs
 - by presence/absence of hemorrhage
 - by presence/absence of fracture
 - by presence/absence of anemia
 - by presence/absence of hypoxia.
 - by presence/absence of intracranial lesions
- b) To describe separately the incidence of a) anemia and b) hypoxia, the incidence of AEs including all AEs, ADRs, grade 3-5 AEs, grade 3-5 ADRs, SAEs and SADR
- c) To describe the proportion of subjects of intracranial hemorrhage AEs including all AEs, ADRs, grade 3-5 AEs, grade 3-5 ADRs, SAEs and SADR with or without pre-existing intracranial lesions
- d) To describe the overall incidence and outcomes of AEs, ADRs, grade 3-5 AEs, grade 3-5 ADRs, SAEs, SADR, unexpected SAEs, and unexpected SADR;
- e) For hemorrhage AEs, fracture AEs, anemia AEs, hypoxia AEs, all AEs, All SAEs, All ADRs, all SADR:
 - To describe the proportion of subjects who interrupt drug due and the reasons for drug interruption;
 - To describe the proportion of subjects who discontinue drug and the reasons for drug discontinuation;
 - To describe the proportion of subjects with dose reduction and the reasons for dose reduction;
- f) To describe a) objective response rate (ORR) and b) disease control rate (DCR) in subjects that receive the recommended dose.

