6.5 Study Method

Procedures and activities during this study are outlined in [Table 1](#).

Table 1 Schedule of Activities

Timing of implementation Item	Before the start of administration	Observation Period (Up to a Maximum of 12 Months)				Note
		During administration	At the end of administration	From the end of administration until 30 days after the end of administration	End of observation phase (12 months)	
Informed consent / Privacy statement	X					
Inclusion/Exclusion criteria review	X					
Subject characteristics and indication(s) for use	X					
Medical history and Concurrent condition	X					For liver dysfunction, The Child-Pugh classification (Table 2) is used. Points are assigned to each item, and the total score is classified based on Table 3 .
Condition of RCC before belzutifan Administration	X					
Prior Treatment for RCC before belzutifan Administration	X					

Timing of implementation Item	Before the start of administration	Observation Period (Up to a Maximum of 12 Months)				Note
		During administration	At the end of administration	From the end of administration until 30 days after the end of administration	End of observation phase (12 months)	
Treatment with belzutifan		X	X			
Concomitant medications/Concomitant therapies		X	X	X		Concomitant medications/therapies for RCC used during belzutifan administration period, and AE/ prophylactic use during the administration period or within 30 days after discontinuation of belzutifan.

Timing of implementation Item	Before the start of administration	Observation Period (Up to a Maximum of 12 Months)				Note
		During administration	At the end of administration	From the end of administration until 30 days after the end of administration	End of observation phase (12 months)	
Effectiveness		X	X	X	X	Effectiveness assessments will be conducted until disease progression, initiation of other anti-cancer therapies, death, or loss to follow-up, whichever occurs first. However , the maximum assessment period will not exceeding the observation period [12 months (52 weeks) from the first belzutifan treatment date].
Status on the date of last observation					X	At 12 months (52 weeks) from the start of belzutifan administration; however, in cases where death or lost to follow-up occurs within 12 months from the start of belzutifan administration, the date of confirmation of these events shall be considered.
Adverse Event		X	X	X		Refer to Table 4 , Table 5 and Table 6 for supplementary notes related to AEs.

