6.7.2 Secondary endpoints

Safety items

The following will be set as endpoints for the risk of anemia and separately hypoxia using investigator reported adverse events, including frequency and severity of these events:

- AEs, SAEs, Grade 3-5 AEs
- ADRs, SADRs, Grade 3-5 ADRs

The following will be set as endpoints for the risk of intracranial hemorrhage with or without pre-existing intracranial lesions using investigator reported AEs, including frequency and severity of these events:

- AEs, SAEs, grade 3-5 AEs,
- ADRs, SADRs grade 3-5 ADRs

The following will be set as endpoints for overall safety using investigator reported adverse events, including frequency and severity of these events:

- AEs, SAEs, Grade 3-5 AEs, Unexpected SAEs
- ADRs, SADRs, Grade 3-5 ADRs, Unexpected SADRs,

Effectiveness items

The following will be calculated.

- Overall Response Rate (ORR): Complete Response (CR) or Partial Response (PR)
- Disease Control Rate (DCR): CR, PR, or Stable Disease (SD)

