6.9.3 Secondary Objective analysis

- 1) Patient demographic and clinical characteristics will be analyzed and reported as noted above according to whether they are a categorical or continuous variables for:

- a) the registered subjects
- b) the safety evaluation group
- c) by presence/absence of any adverse event
- d) by presence/absence of hemorrhage
- e) by presence/absence of fracture
- f) by presence/absence of anemia
- g) by presence/absence of hypoxia
- h) by presence/absence of intracranial lesions

- 2) The incidence of anemia AEs and the incidence hypoxia AEs, including all AEs, ADRs, grade 3-5 AEs, grade 3-5 ADRs, SAEs, and SADR will be separately analyzed and reported as categorical variables

- 3) The incidence of intracranial hemorrhage AEs with or without pre-existing intracranial lesions, including all AEs, ADRs, grade 3-5 AEs, grade 3-5 ADRs, SAEs, and SADR reported by the investigator will be separately analyzed and reported as categorical variables
- 4) The incidence of overall safety events reported by investigator, including all AEs, ADRs, grade 3-5 AEs, grade 3-5 ADRs, SAEs, SADR, unexpected SAEs, and unexpected SADR, will be analyzed and reported as categorical variables
- 5) The following will be analyzed and reported as categorical variables for a) hemorrhage AEs, b) fracture AEs, c) anemia AEs, d) hypoxia AEs, e) all AEs, f) all SAEs, g) all ADRs and h) all SADR reported by the investigator:
 - the proportion of subjects who interrupt drug due and the reasons for drug interruption
 - the proportion of subjects who discontinue drug and the reasons for drug discontinuation
 - the proportion of subjects with dose reduction and the reasons for dose reduction
- 6) The following will be analyzed and reported as categorical variables for the effectiveness analysis population based on the investigator's overall assessment after completion of administration, as detailed in the stand-alone statistical analysis plan:
 - ORR: best overall response rate (CR or PR)
 - DCR: best response rate of (CR, PR, SD)

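### Intracranial hemorrhage is to be analysed by lesions present before treatment, but no listed item explicitly records intracranial lesion status before first dose

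*Protocol*

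**What the plan says.** Three places in the protocol define the split by a baseline attribute. Section 5.2, item c), describes intracranial hemorrhage "with or without pre-existing intracranial lesions". Section 6.7.2 sets "endpoints for the risk of intracranial hemorrhage with or without pre-existing intracranial lesions". Section 6.9.3, item 3), analyses the same split.

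The collection list in section 6.6 names intracranial lesions once, under the status on the date of last observation: "Presence or absence of intracranial lesions during the observation period". Section 6.5.4 fixes that window: "The observation period is defined as 12 months (52 weeks) from the start date of the administration". Table 1 in section 6.5 places the status "At 12 months (52 weeks) from the start of belzutifan administration", or at confirmed death or loss to follow-up if earlier. The item lists no date of detection.

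One pre-treatment item bears on the question. Under the condition of RCC before administration, section 6.6 collects "Site of recurrence or metastasis at most recent diagnosis". Medical history is also collected before treatment, for selected conditions and others, but intracranial lesions are not among those named.

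Section 5.2, item a), and section 6.9.3, item 1) h), also group patient characteristics by intracranial lesions, this time without the qualifier pre-existing.

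**The concern.** The analysis needs lesion status at first dose. The one dedicated item describes a window that opens at first dose and is filled in after any bleed has happened. Imaging prompted by a bleed can reveal a lesion nobody knew of, and new brain metastases can appear on treatment. Without a date, neither can be told apart from a lesion that was there at the start.

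If that item became the stratifier, group membership would depend partly on the outcome. The survey might then report that intracranial bleeding occurs only, or mainly, in subjects with lesions when part of that pattern comes from when lesions were looked for. Hemorrhage is an important potential risk in the Japanese risk management plan, and section 3 says the survey's results feed the review of that plan.

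**Working it through.** **1. The plan's own figure.** Section 6.3 requires 403 subjects to see at least 11 Grade 3 or higher hemorrhages at 3.8% with over 90% probability. The exact binomial tail P(X ≥ 11) is 0.9005 for n = 403 and 0.8988 for n = 402, so 403 is reproduced. The point made here does not depend on it. It does give scale: 403 × 0.038 ≈ 15 Grade 3 or higher hemorrhages at all sites. The protocol gives no rate for intracranial bleeds and no lesion prevalence, so steps 3 and 4 rest on assumed values.

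**2. Timing, side by side (protocol).**

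| Place | Lesion status meant or collected | When |
|---|---|---|
| 5.2 c), 6.7.2, 6.9.3 item 3) | Pre-existing | Before first dose |
| 6.6, last-observation status | Present or absent in the observation period, undated | Window from first dose; recorded at 12 months, death or loss to follow-up |
| 6.6, condition of RCC | Site of recurrence or metastasis | Before treatment, as of the most recent diagnosis |
| 6.6, medical history | Selected conditions and others | Before treatment; intracranial lesions not named |
| 6.6, tests including imaging | Dated findings | Only where related to an adverse event (Table 1) |

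The imaging item may date a lesion in a subject who bled. It cannot classify the subjects who did not bleed, and they make up most of each denominator. The windows also differ: the lesion item runs over the whole observation period, whereas intracranial hemorrhage is recorded up to 30 days after the last dose. A lesion that appears after the bleed window has closed would still count as present.

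**3. Small-count illustration.** Assumed: 403 subjects, 40 with baseline lesions, 4 intracranial bleeds, 2 of them in lesion-free subjects. The variants use 18 new lesions among the 361 lesion-free subjects who do not bleed (18/361 = 5.0%).

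| Scenario | With lesion | Without lesion |
|---|---|---|
| True baseline split | 2/40 = 5.0% | 2/363 = 0.55% |
| One lesion-free bleed moved | 3/41 = 7.3% | 1/362 = 0.28% |
| Both moved | 4/42 = 9.5% | 0/361 = 0% |
| None moved, 18 new lesions in non-bleeders | 2/58 = 3.4% | 2/345 = 0.58% |
| One moved, 18 new lesions | 3/59 = 5.1% | 1/344 = 0.29% |
| Both moved, 18 new lesions | 4/60 = 6.7% | 0/343 = 0% |

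Both moved is the extreme case: every lesion-free bleed is reclassified.

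**4. No true difference.** Let b be baseline lesion prevalence, r a bleed risk equal in both groups, f the share of lesion-free bleeds later flagged as having a lesion, and g the share of lesion-free non-bleeders with a new lesion. With L = 403b and U = 403 − L:

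- with-lesion rate = (Lr + fUr) / (L + fUr + gU(1 − r))
- without-lesion rate = (Ur − fUr) / (U − fUr − gU(1 − r))

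For b = 10%, r = 1%, f = 25%, g = 0:

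- with lesion: (0.403 + 0.907) / (40.3 + 0.907) = 3.18%
- without lesion: 2.720 / 361.79 = 0.75%
- ratio 4.2, where the truth is 1.0

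With g = 5% the rates are 2.21% and 0.79%, ratio 2.8. Over b = 5 to 15%, r = 1 to 2% (about 4 to 8 bleeds), f = 25 to 50% and g = 0 to 5%, the ratio runs from about 2.3 to 19.

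The direction is not fixed. With f = 0 and g = 5% (b = 10%, r = 1%), the rates are 0.403/58.25 = 0.69% and 3.627/344.75 = 1.05%, ratio 0.66. If a baseline item is the stratifier, then f = g = 0 and this distortion does not arise.

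**The case against.** The strongest reply is that no section makes the observation-period item the stratifier. Section 6.9.3, item 3), asks for pre-existing lesions and names no source. Mapping collected items to analysis variables is ordinary content for the statistical analysis plan, which is not shown. The observation-period item may serve section 6.9.3, item 1) h), which drops the qualifier. This stands. A reader might infer that lesions found because of a bleed will be counted as the risk factor; the protocol does not say so, and the point holds only conditionally.

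The second reply is that pre-treatment data exist. The metastasis-site item is scheduled before administration, and prior radiotherapy, prior surgery, medical history, hemorrhage-related comorbidities, dated imaging and sponsor queries could help classify individual bleeds. This stands in part. None of these items asks explicitly about intracranial lesions before first dose. The site item is tied to the most recent diagnosis and does not cover non-metastatic lesions. The event-related items do not reach subjects without a bleed. A statistical analysis plan can choose among collected variables, but it cannot supply one that was not collected.

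Two further inferences fail. An always-inflated with-lesion rate is not established, since new lesions in non-bleeders dilute it. Nor does the text support the idea that a bleed would itself be entered as a lesion, since section 6.6 lists the two as separate items.

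Finally, this is one secondary description in a single-arm survey with no hypothesis testing, and section 6.10 already asks for cautious interpretation. That limits the severity.

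**Conclusion.** The point holds in a limited form. The objective, endpoint and analysis require lesion status before first dose. No listed item explicitly records it, and the protocol does not say which item defines pre-existing. Known brain metastases may be recoverable from the metastasis-site item; other lesions are not reliably captured.

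The harm depends on the observation-period item being used as the stratifier. In that case, with 4 to 8 intracranial bleeds and the other inputs of step 4 (all assumed), a true ratio of 1.0 could appear as about 2.3 to 19. If only new lesions in non-bleeders matter, it could fall below 1. These figures show sensitivity and are not forecasts.

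A reader might take this as a defect of the main safety results. It is not: the primary endpoints, the sample size of 403 and the capture and reporting of bleeds are unaffected. It should be fixed, because the objective cannot be answered reliably as the items stand.

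**What to change.** - **Add one eCRF item**, taken from the chart, to the block on the condition of RCC before belzutifan administration: intracranial lesion known before first dose (yes, no, not imaged), with type and date of the last imaging before first dose.
- **Name it as the stratifier** for section 5.2 c), section 6.7.2 and section 6.9.3, item 3).
- **Keep the observation-period item** to describe new lesions, and add a date of detection.
- **State in section 6.9.3, item 1) h)**, and in the matching line of section 5.2 a), whether the grouping means baseline or observation-period status.

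The cost is one more chart item per subject, one date field, a few words of text and a not-imaged category to report. No imaging is added and the sample size does not change. It is cheapest before registration opens, planned for April 2026.
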